1 ADVERSE EVENTS

An ***Adverse Event (AE)*** is defined as any new untoward medical occurrence or worsening of a pre-existing medical condition in a patient or clinical investigation subject administered an investigational (medicinal) product and that does not necessarily have a causal relationship with this treatment. An AE can therefore be any

unfavorable and unintended sign (including an abnormal laboratory finding, for example), symptom, or disease temporally associated with the use of investigational product, whether or not considered related to the investigational product.

Adverse events can be spontaneously reported or elicited during open-ended questioning, examination, or evaluation of a subject. (In order to prevent reporting bias, subjects should not be questioned regarding the specific occurrence of one or more AEs.)

1.1 **Serious Adverse Events**

A ***serious AE (SAE)*** is any untoward medical occurrence that at any dose:

- results in death
- is life-threatening (defined as an event in which the subject was at risk of death at the time of the event; it does not refer to an event which hypothetically might have caused death if it were more severe)
- requires inpatient hospitalization or causes prolongation of existing hospitalization (see **NOTE** below)
- results in persistent or significant disability/incapacity
- is a congenital anomaly/birth defect
- is an important medical event (defined as a medical event(s) that may not be immediately life-threatening or result in death or hospitalization but, based upon appropriate medical and scientific judgment, may jeopardize the subject or may require intervention [eg, medical, surgical] to prevent one of the other serious outcomes listed in the definition above.) Examples of such events include, but are not limited to, intensive treatment in an emergency room or at home for allergic bronchospasm; blood dyscrasias or convulsions that do not result in hospitalization.)

Suspected transmission of an infectious agent (eg, any organism, virus or infectious particle, pathogenic or non-pathogenic) via the study drug is an SAE.

Although pregnancy, overdose, and cancer are not always serious by regulatory definition, these events must be handled as SAEs. (See Section 6.1.1 for reporting pregnancies.)

NOTE:

The following hospitalizations are not considered SAEs in clinical studies:

- a visit to the emergency room or other hospital department < 24 hours, that does not result in admission (unless considered "important medical event" or event life threatening)
- elective surgery, planned prior to signing consent
- admissions as per protocol for a planned medical/surgical procedure
- routine health assessment requiring admission for baseline/trending of health status (eg, routine colonoscopy)
- medical/surgical admission for purpose other than remedying ill health state and was planned prior to entry into the study. Appropriate documentation is required in these cases
- admission encountered for another life circumstance that carries no bearing on health status and requires no medical/surgical intervention (eg, lack of housing, economic inadequacy, care-giver respite, family circumstances, administrative).

1.1.1 Serious Adverse Event Collection and Reporting

Following the subject's written consent to participate in the study, all SAEs, whether related or not related to study drug, must be collected, including those thought to be associated with protocol-specified procedures. All SAEs must be collected that occur during the screening period and within 30 days of discontinuation of dosing. If applicable, SAEs must be collected that relate to any later protocol-specified procedure (eg, a follow-up skin biopsy).

The investigator should report any SAE occurring after these time periods that is believed to be related to study drug or protocol-specified procedure.

An SAE report should be completed for any event where doubt exists regarding its status of seriousness.

If the investigator believes that an SAE is not related to the study drug, but is potentially related to the conditions of the study (such as withdrawal of previous therapy, or a complication of a study procedure), the relationship should be specified in the narrative section of the SAE Report Form.

SAEs, whether related or not related to study drug, and pregnancies must be reported within 24 hours. SAEs must be recorded on the SAE Report Form; pregnancies on a Pregnancy Surveillance Form (electronic or paper forms).

For studies capturing SAEs/pregnancies through electronic data capture (EDC), electronic submission is the required method for reporting. The paper forms should be used and submitted immediately, only in the event the electronic system is unavailable for transmission. When paper forms are used, the original paper forms are to remain on site.

If only limited information is initially available, follow-up reports are required. (Note: Follow-up SAE reports should include the same investigator term(s) initially reported.)

If an ongoing SAE changes in its intensity or relationship to study drug or if new information becomes available, a follow-up SAE report should be sent within 24 hours using the same procedure used for transmitting the initial SAE report.

All SAEs should be followed to resolution or stabilization.

1.2 Nonserious Adverse Events

A **nonserious adverse event** is an AE not classified as serious.

1.2.1 Nonserious Adverse Event Collection and Reporting

The collection of nonserious AE information should begin at initiation of study drug. Nonserious AE information should also be collected from the start of a placebo lead-in period or other observational period intended to establish a baseline status for the subjects.

Nonserious AEs should be followed to resolution or stabilization, or reported as SAEs if they become serious (see Section 6.1.1). Follow-up is also required for nonserious AEs that cause interruption or discontinuation of study drug, or those that are present at the end of study treatment as appropriate. All identified nonserious AEs must be recorded and described on the nonserious AE page of the CRF (paper or electronic).

Completion of supplemental CRFs may be requested for AEs and/or laboratory abnormalities that are reported/identified during the course of the study.

1.3 Laboratory Test Abnormalities

The following laboratory abnormalities should be captured on the nonserious AE CRF Page or SAE Report Form (paper or electronic) as appropriate:

- Any laboratory test result that is clinically significant or meets the definition of an SAE
- Any laboratory abnormality that required the subject to have the study drug discontinued or interrupted
- Any laboratory abnormality that required the subject to receive specific corrective therapy.

It is expected that wherever possible, the clinical, rather than the laboratory term would be used by the reporting investigator (eg, anemia versus low hemoglobin value).

1.4 Pregnancy

If, following initiation of the investigational product, it is subsequently discovered that a study subject is pregnant or may have been pregnant at the time of investigational product exposure, including during at least 6 half lives after product administration, the investigational product will be permanently discontinued in an appropriate manner (eg, dose tapering if necessary for subject safety). Protocol-required procedures for study discontinuation and follow-up must be performed on the subject unless contraindicated by pregnancy (eg, x-ray studies). Other appropriate pregnancy follow-up procedures should be considered if indicated.

The investigator must immediately notify the Medical Monitor of this event and complete and forward a Pregnancy Surveillance Form to within 24 hours and in accordance with SAE reporting procedures described in Section 6.1.1.

Follow-up information regarding the course of the pregnancy, including perinatal and neonatal outcome and, where applicable, offspring information must be reported on the Pregnancy Surveillance Form.

If, following initiation of the investigational product, it is subsequently discovered that a study subject is pregnant or may have been pregnant at the time of investigational product exposure, including during at least 6 half lives after product administration, the investigational product will be permanently discontinued in an appropriate manner (eg, dose tapering if necessary for subject safety). Protocol-required procedures for study discontinuation and follow-up must be performed on the subject unless contraindicated by pregnancy (eg, x-ray studies). Other appropriate pregnancy follow-up procedures should be considered if indicated.

The investigator must immediately notify the Medical Monitor of this event and complete and forward a Pregnancy Surveillance Form within 24 hours and in accordance with SAE reporting procedures described in Section 6.1.1.

Follow-up information regarding the course of the pregnancy, including perinatal and neonatal outcome and, where applicable, offspring information must be reported on the Pregnancy Surveillance Form.

Not applicable.

Not applicable.

Any pregnancy that occurs in a female partner of a male study participant should be reported to the sponsor. Information on this pregnancy will be collected on the Pregnancy Surveillance Form.

1.5 Overdose

All occurrences of overdose must be reported as SAEs (see Section 6.1.1 for reporting details).

An overdose is defined as the accidental or intentional administration of any dose of a product that is considered both excessive and medically important. All occurrences of overdose must be reported as an SAE (see Section 6.1.1 for reporting details.).

1.6 Other Safety Considerations

Any significant worsening noted during interim or final physical examinations, electrocardiograms, x-rays, and any other potential safety assessments, whether or not these procedures are required by the protocol, should also be recorded as a nonserious or serious AE, as appropriate, and reported accordingly.

2 DATA MONITORING COMMITTEE AND OTHER EXTERNAL COMMITTEES

Not applicable

8. Measurements: Blood glucose from the arterial line will be measured at baseline (prior to exenatide), hourly during the 48 hour exenatide infusion per protocol (table 2) and continue for an additional 24 hours following exenatide discontinuation. The continuous glucose monitor will measure the interstitial glucose level every 5 minutes beginning at baseline (prior to exenatide) until 24 hours following exenatide discontinuation. Blood samples for pharmacokinetic analysis will be collected in serum separator tubes at 0, 12, 24, 36 and 48 hours after the start of the infusion. Eight-hour urine collections will be obtained on a daily basis for 72 hours (48 hours during study drug infusion and an additional 24 hours during follow-up after study drug is discontinued). Microdialystate concentrations will be collected at baseline (prior to exenatide), and hourly during the 48-hour exenatide infusion for parameters of energy metabolism (glucose, pyruvate, lactate, lactate:pyruvate ratio), glutamate (marker of cerebral ischemia), and glycerol (marker of cell membrane degradation) and for an additional 24 hours following study drug discontinuation. Blood pressure will be measured continuously throughout the study period. Intracranial pressure (ICP) will be measured continuously during the exenatide infusion. Intracranial pressure values will be recorded at baseline (prior to exenatide) and daily mean ICP and cerebral perfusion pressure values will be reported. Baseline demographic information (e.g. gender, age, ethnicity) and disease severity information [e.g. Glasgow coma score, SOFA score (Sequential Organ Failure Assessment), Hunt Hess classification, Fisher grade, primary diagnosis, past medical history (including measurement of hemoglobin A1c), neurologic exam/computed tomography scan abnormalities] will be collected. The ICU day of study drug administration will be recorded and the total hospital and ICU lengths of stay will be recorded.

9. Data Management: Each participant will be assigned a unique identification number. No personal identification will be used. All study files will be stored in locked cabinets in the Principal Investigator's office in the Pharmacy Administration Department. Data will be entered into the study database using double entry (entry and verification) and will be checked for missing or ineligible responses.

10. Outcomes

10.1 The following feasibility endpoints are based upon prior literature (Nice-Sugar and Exenatide Study in the Cardiac ICU):

Proportion of patients experiencing severe hypoglycemia (<40 mg/dL), Proportion of patients achieving plasma glucose goal (110-180 mg/dL), Proportion of patients experiencing nausea requiring discontinuation of exenatide therapy

10.2 The following descriptive endpoints are included for describing experience with exenatide use in the NSICU population:

Average blood glucose value during exenatide infusion (48 hours), percent time in glucose range (48 hours), mean time to reach plasma glucose goal (110-180 mg/dL), variability outcome (SD)-MADGE, mean insulin use required (units/kg body weight), proportion of subjects requiring rescue insulin infusion protocol, number of hypoglycemic episodes (<80 mg/dL)/total number of glucose measurements (48 hours), number of subjects with >1 hypoglycemic episode (<80 mg/dL)/total number of subjects (48 hours), correlation of exenatide concentrations with creatinine clearance during infusion, elimination rate constant and area under the concentration-time curve utilizing concentrations after discontinuation of infusion, side effects and adverse events (AEs and SAEs), average daily ICP and CPP during study drug infusion, number of hypotensive episodes (SBP<100 mmHg) (48 hours), number of subjects with >1 hypotensive episode/total number of subjects (48 hours). Other adverse effects will be collected specifically assessing any alterations in gastric motility.

In patients receiving invasive intracranial multimodal monitoring as part of their standard of care, the following endpoints associated with exenatide use will be described:

Percent time outside of range for energy metabolism (glucose <0.7 mmol/L and lactate:pyruvate ratio > 40), glutamate (marker of cerebral ischemia), and glycerol (marker of cell membrane degradation) parameters (48 hours).

Based upon prior literature, the prespecified criteria for determining feasibility include the following: 1) no more than 6 patients (25%) experiencing severe hypoglycemia (<40 mg/dL); 2) at least 18 patients (75%) achieving the plasma glucose goal (110-180 mg/dL); 3) no more than 6 patients (25%) experiencing nausea leading to exenatide discontinuation. These criteria will be utilized to determine whether a future efficacy trial will be pursued.

11. Sample size and justification: A sample size was determined using prior exenatide in critically ill patients studies and patient screening information at our site. Based upon this data, we determined to enroll 24 patients who complete 48 hours of exenatide infusion and continuous glucose monitoring. In eligible patients, cerebral microdialysis monitoring will also be performed. It is estimated based on proposed eligibility criteria that 24% (n = 200) patients admitted to the NSICU will be eligible for enrollment annually. With an approximate rate of enrollment at 15 – 20%, we are confident we could enroll 30 – 40 subjects annually.

12. Data analysis plan: Prior to analysis, data will be examined for errors, outliers, and asymmetry. When appropriate, transformations will be used to reduce asymmetry. An intent-to-treat analysis (defined as all individuals consented in the study) will be utilized. Descriptive statistics will be performed. Data will be expressed as means \pm standard error (SE) or success rates and corresponding 95%CI for continuous and

dichotomous outcomes, respectively. Analyses will be completed using the statistical software package SAS, version 9.2 (SAS institute, Cary, North Carolina).

13. Ethical consideration: The consent procedures will be reviewed and approved by the Institutional Review Board. All subjects will provide written informed consent via proxy. The informed consent process will allow the proxy to gain an in-depth knowledge of the study purposes and procedures and allow them to make informed decisions about willingness to proceed. Participation is voluntary. The proxy will be encouraged to ask questions and will be assessed for adequate understanding.

Exenatide required: yes

Placebo required: no

Clinical study duration of treatment: Subjects will be exposed to exenatide treatment for 48 hours.

Clinical study dosing schedule and frequency: exenatide 50 ng/min for 30 minutes, start exenatide infusion 25 ng/min x 48 hours

Clinical study number of sites: one

Clinical study expected number of subjects screened: It is estimated based on proposed eligibility criteria that 24% (n = 200) patients admitted to the NSICU will be eligible for enrollment annually with an approximate rate of enrollment at 15-20%.

Clinical study expected number of subjects enrolled: 24

Clinical study expected number of subjects to complete study: 24

Planned Study Start Date: January 1, 2015

Planned Study End Date: June 30, 2016

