1. Subjects: Adult patients (≥ 18 years) with two consecutive blood glucose readings of > 150 mg/dL and ≤ 300 mg/dL will be eligible for inclusion in this study. The study population will be limited to those with acute brain injury resulting in admission to the NSICU for an anticipated length of stay >48 hours and who will not have planned steroid use post-operatively. Patients with imminent brain death or refractory intracranial hypertension will not be enrolled. Pregnant (verified by urine or serum pregnancy test within 24 hours of initiation of exenatide infusion) or lactating females, and those with a history of type 1 diabetes mellitus, pancreatitis or risk factors for acute pancreatitis (i.e. ethanol abuse, gall stones), renal insufficiency (CrCL < 45 mL/min), gastroparesis, surgery on stomach, esophageous, or duodenum or those with organ transplantation will be excluded. Additionally, those presenting with diabetic ketoacidosis or hyperosmolar hyperglycemic nonketotic syndrome will be excluded. Individuals receiving steroids or planned post-operative administration, insulin infusion within 3 hours of study drug administration, long acting insulin or sulfonylureas within 24 hours of study drug administration, another investigational drug or device, or those with known allergy to any of the study protocol drugs will be excluded. Recruitment will continue until 24 subjects receive study drug and complete the study protocol.

2. Glycemic Control Protocol: All study related protocols will be conducted in the Neuroscience Intensive Care Unit (NSICU). All patients admitted to the NSICU and that meet the eligibility criteria will be approached for consent to the study. Study drug will only be administered to those subjects providing consent via legally authorized representative and meeting glycemic thresholds. The study nurse will initiate the exenatide infusion

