<70	
Discontinue exenatide infusion.
 
Give 25 mL of dextrose 50% (1/2 amp) IVP – Recheck glucose in 5 minutes and notify physician.
 
Check glucose hourly after hypoglycemia is resolved.
 
When 2 in a row hourly glucose checks are greater than 109 restart exenatide infusion at 25 ng/min
 
Notify physician when glucose greater than 80 mg/dL
 
Monitor blood pressure continuously during infusion (if SBP <100 mmHg, contact physician)

80-109	
Temporarily discontinue exenatide infusion
 
Check glucose hourly
 
When glucose greater than 109 restart exenatide infusion at 25 ng/min
 
Note: If 3 in a row hourly checks are less than 110 restart protocol from beginning. Change glucose check to q4h and exenatide protocol for second glucose greater than 180 mg/dL
 
Monitor blood pressure continuously during infusion (if SBP <100 mmHg, contact physician)

110-180	Continue exenatide infusion per protocol Check glucose hourly Monitor blood pressure continuously during infusion (if SBP<100 mmHg, contact physician)
181-216	1 st hourly glucose check (=1 hour since exenatide initiation): continue exenatide infusion protocol ≥2 nd hourly glucose check (≥2 hours since exenatide initiation): Give 2 units of formulary available rapid acting insulin subcutaneously and continue exenatide infusion protocol Check glucose hourly Monitor blood pressure continuously during infusion (if SBP <100 mmHg, contact physician)
217-252	1 st hourly glucose check (=1 hour since exenatide initiation): continue exenatide infusion protocol ≥2 nd hourly glucose check (≥2 hours since exenatide initiation): Give 4 units of formulary available rapid acting insulin subcutaneously and continue exenatide infusion protocol Check glucose hourly Monitor blood pressure continuously during infusion (if SBP <100 mmHg, contact physician)
253-300	1 st hourly glucose check (=1 hour since exenatide initiation): continue exenatide infusion protocol ≥2 nd hourly glucose check (≥2 hours since exenatide initiation): Give 6 units of formulary available rapid acting insulin subcutaneously and continue exenatide infusion protocol Check glucose hourly Monitor blood pressure continuously during infusion (if SBP <100 mmHg, contact physician)
>300	Recheck blood glucose within 5 minutes If confirmed, contact physician to discontinue exenatide and initiate rescue insulin infusion protocol (NSICU insulin infusion protocol)

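### The mean time to glucose goal has no rule for patients who stop exenatide or start rescue insulin before reaching goal

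*Combined protocol and SAP*

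**What the plan says.** Section 10.2 names the endpoint, "mean time to reach plasma glucose goal (110-180 mg/dL", and says no more about it. It gives no time origin, no glucose source and no treatment of patients who do not reach goal.

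The only analysis rule is in Section 12: "Data will be expressed as means \pm standard error (SE) or success rates and corresponding 95%CI for continuous and" dichotomous outcomes respectively. The analysis set is given there too: "An intent-to-treat analysis (defined as all individuals consented in the study) will be utilized". Section 12 has no censoring rule, competing-event rule, assigned value or time-to-event method. Its provision for transformations deals with asymmetry, not with times that were never observed.

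The plan does provide for patients who leave exenatide early. For a confirmed glucose above 300 mg/dL, Table 2 says: "If confirmed, contact physician to discontinue exenatide and initiate rescue insulin infusion protocol". The feasibility criteria that close Section 10 ask for "at least 18 patients (75%) achieving the plasma glucose goal (110-180 mg/dL" and "no more than 6 patients (25%) experiencing nausea leading to exenatide discontinuation". Section 10.2 counts the rescue infusion as a proportion of its own, without linking it to time to goal.

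Two further statements matter. Section 8 has arterial glucose measured hourly during the infusion and for 24 hours after exenatide is discontinued. Section 1 (Subjects) says "Recruitment will continue until 24 subjects receive study drug and complete the study protocol", and Section 11 says "we determined to enroll 24 patients who complete 48 hours of exenatide infusion and continuous glucose monitoring".

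**The concern.** A plain mean needs a time for every patient in it. Here some patients may stop or switch treatment before the event, and the plan does not say what they contribute. Two analysts could both follow the plan and report different numbers.

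Both natural readings mislead. A mean over those who reached goal on exenatide looks faster than the regimen is, and it does not match an analysis set of all consented individuals. A mean that includes times reached after the switch credits exenatide with what the rescue infusion did. The stake is how the regimen's speed of control is described. The decision on a later efficacy trial does not turn on it, because Section 10 ties that decision to the three feasibility criteria.

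**Working it through.** **The plan's own figures.** 0.75 x 24 = 18 and 0.25 x 24 = 6, as stated. Criterion 2 can therefore be met with up to six patients not reaching goal. Section 10 gives no expected time to goal and no standard deviation, so everything below is illustration.

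**The two readings side by side.**

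1. *Non-reachers left out.* The recruitment rule makes this easy to fall into. Enrolment runs until 24 patients complete, and completion means 48 hours of infusion, so a patient switched to rescue insulin is not a completer and can be replaced. The mean is then conditional on success.
2. *Later times counted.* Section 8 supplies glucose readings for 24 hours after the stop, so a switched patient can have a time to 110-180 mg/dL, reached under the rescue infusion.

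**Size under reading 1, model A.** Assume an exponential time to goal and a 48-hour window, with share p reaching goal inside it.

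- Rate = -ln(1 - p)/48
- Mean over reachers = 1/rate - 48(1 - p)/p
- Mean restricted to 48 h over everyone = p/rate

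For p = 0.75: 1/rate = 48/1.3863 = 34.62 h. Mean over reachers = 34.62 - 16 = 18.6 h. Restricted mean = 0.75 x 34.62 = 26.0 h. Shortfall = 1 - 18.6/26.0 = 28%.

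**Size under reading 1, model B.** Assume an exponential time to goal with underlying mean m, and an independent competing stop set so that goal comes first in a share s. The stop hazard is (1/m)(1 - s)/s, so the mean over reachers is s x m before the 48-hour cut-off. For m = 6 h this is 0.75 x 6 = 4.5 h and 0.9 x 6 = 5.4 h. For m = 12 h the cut-off matters a little, and the values below are simulated.

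| Assumption | Reach goal | Mean over reachers | Comparator | Shortfall |
|---|---|---|---|---|
| A | 75% | 18.6 h | 26.0 h | 28% |
| A | 87.5% | 16.2 h | 20.2 h | 20% |
| A | 95% | 13.5 h | 15.2 h | 11% |
| B, m = 6 h | 75% | 4.5 h | 6 h | 25% |
| B, m = 6 h | 90% | 5.4 h | 6 h | 10% |
| B, m = 12 h | 74.6% | 8.75 h | 12 h | 27% |
| B, m = 12 h | 89% | 10.22 h | 12 h | 15% |

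The comparator is the 48-hour restricted mean in A and the underlying mean without stopping in B, so the two blocks do not estimate the same quantity. They agree in direction and roughly in size. If every patient reaches goal first, the shortfall is zero.

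**Two further influences.** Entry requires glucose above 150 and up to 300 mg/dL, which overlaps the goal at 151-180 mg/dL. A patient starting there is at goal at time zero, which also shortens the mean. Table 2 gives subcutaneous insulin for 181-300 mg/dL from the second hourly check, so some insulin effect is present even without the rescue infusion.

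**The case against.** The strongest reply is that the plan nowhere says these patients are dropped. Glucose is followed for 24 hours after discontinuation, so many who stop or switch may have an observed time. This stands. A reader might infer that such patients have no value at all and that the mean describes only successes. That is one reading of a silent plan, not its stated rule.

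A reader might also infer from criterion 2 that the plan expects six failures. With an assumed 4 h among reachers, that would set 4 h against (18 x 4 + 6 x 48)/24 = 15 h. The arithmetic is right, but 18 of 24 is a pass threshold and not a forecast, the 4 h is assumed, and six patients placed at 48 h is the worst case that still passes. With entry overlapping the goal, hourly checks and sliding-scale insulin, a patient treated for the full 48 hours would miss goal only if every reading were out of range, provided that one in-range reading counts as reaching goal (the plan does not say). Patients who stop early are the likelier source of non-reachers, and nothing in the documents says how many there will be.

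The endpoint is also descriptive, and the proportion reaching goal, the proportion rescued, percent time in range and insulin use are reported beside it. Non-reachers are therefore not hidden. This stands and limits the importance of the point.

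Finally, a competing-risks analysis may look heavy for about 24 patients, when a median with a stated denominator might do. This carries less weight. If every treated patient is followed to goal, stop or 48 hours, the cumulative incidence at a fixed time is simply the number who have reached goal by then divided by the number treated.

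**Conclusion.** The concern holds as a gap in definition combined with an unsuitable summary statistic. A plain mean does not suit an event that some patients may not reach on treatment, and the plan leaves open whether the result is conditional on success or mixed with rescue insulin.

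Its size in this trial cannot be derived from the documents. If non-reachers are left out, the assumed exponential models give a mean about 25-28% too short at 75% reaching goal, about 10% (15% in one scenario) at about 90-95%, and no shortfall if all reach goal. Model B also assumes that stopping is independent of the time to goal. That is doubtful for rescue, which is triggered by high glucose. For the same reason, simply censoring at rescue would be informative.

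The documents do not support a stronger conclusion that the mean is certainly biased, that it is off several-fold, or that the feasibility decision is affected. The change is worth making, at moderate priority.

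**What to change.** In Sections 10.2 and 12, replace the mean with a time-to-event description:

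- **Population and origin:** all treated patients, from the start of infusion. Consented patients never given drug have no time origin, so state that this endpoint departs from the all-consented set. Include treated patients who do not complete 48 hours.
- **Event:** first hourly arterial reading in 110-180 mg/dL.
- **Competing event:** permanent exenatide stop, or start of the rescue insulin infusion, before goal. Temporary holds do not count.
- **Censoring:** at 48 hours for patients still off goal.
- **Report:** the cumulative incidence, the median if reached, and the proportion at goal at fixed times (for example 6, 12, 24 and 48 h) with 95% CI.
- **Already in range:** report patients at 151-180 mg/dL at infusion start separately, since their time is zero.
- **Label:** describe the result as exenatide plus protocol sliding-scale insulin, because the competing event does not remove the sliding-scale effect.

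The cost is mainly analysis wording. Hourly glucose is already collected, and the infusion stop time is needed anyway to time the 24-hour follow-up. The start time of the rescue infusion should be confirmed as a recorded item, because Section 6 promises medication recording only during study drug infusion. The downside is that the reported time may be less favourable. No treatment rule and no feasibility criterion changes.
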